Chronic disease models also allow health systems to reach out to all smokers, not just those who are seeking treatment and ready to quit. In the US, 80% of smokers are “not ready to quit” in the next 30 days.⁴⁸ From a public health standpoint, an effective intervention for this group may have an even greater impact than programs targeting the minority of smokers who are ready to quit.⁴⁹ Furthermore, few evidence-based treatments are available to help “not ready to quit” smokers.^{21,50,51}

b. Preliminary work supporting the proposed study

In prior work, I developed a text message program called the getReady2Quit program (R2Q) and pilot-tested its feasibility among CHC patients. We recruited smokers at MGH Revere and Charlestown using a proactive recruitment process which consisted of sending a letter from the subject’s PCP notifying them of the study, followed by a single text message invitation to opt-in to R2Q. Among 1,603 smokers, 1,279 (80%) had a mobile number in the EHR and 949 were approved by their PCP for the study. 9% (88 of 949) of smokers opted in to R2Q following the letter and single recruitment text and this included both ready to quit (68%) and not ready to quit smokers (32%). The R2Q pilot model had two components. Part 1 targeted smokers who were ready to quit in the next 30 days by proactively recruiting them to a text message program with content to support them through a quit attempt. Part 2 targeted smokers who were not ready to quit. They were sent novel motivational messages and advice to try a ‘Practice Quit Attempt’. This work demonstrated the feasibility of delivering a text messaging program to primary care patients. Subjects in the feasibility study are being recruited to participate in qualitative interviews to further improve the program design and content prior to the current trial.

c. Study rationale

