This will be a 4 arm randomized controlled trial among 206 smokers who are patients at Massachusetts General Hospital and who receive primary care from a Partners primary care provider. Patients will be proactively recruited from MGH primary care practices. Patients will also be recruited from online advertisements on the Partners Clinical Trials website, from among MGH primary care patients who consent to participate in Research Offers Direct to You, and by referral from the MGH inpatient Tobacco Treatment Service counselors. We will recruit both smokers who are ready to quit smoking in the next 30 days and those who are not planning to quit in the next 30 days. The text message program is tailored to readiness to quit. For those ready to quit in the next 30 days, they will be sent messages based on the SmokeFreeTXT content. For those not ready to quit, we have developed content including motivational advice and tips to try a practice quit attempt for a few hours or days.⁵³ The text message program will also include medication adherence support text messages based on the Information-Motivation-Behavioral Skills model of adherence.⁵⁴ Combination NRT is first-line therapy which is more effective than nicotine patch alone and will be offered to daily smokers, dosed per package instructions.²¹ Smokers who are not ready to quit and who are randomized to one of the two nicotine medication arms will be offered one box of lozenges to try in a practice quit attempt.⁵³

The RC will not be blinded to treatment assignment because he/she will register subjects randomized to the text messaging arms in the text messaging program during the enrollment telephone call to verify receipt of an enrollment confirmation text message ("Hi [First name] Welcome to getReady2Quit (R2Q). Your messages and ratings will start soon. Reply STOP to quit, HELP for info. Msg&DataRatesMayApply"). Randomization will be done by a computer generated random sequence.

b. Procedures for obtaining informed consent (including timing of consent process)

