Finally, the text messaging program will be tailored to the individual and MGH. Text messages will include the telephone number for the MGH tobacco cessation counseling services LivingTobacco-Free which accept self-referrals as well as the number for the Massachusetts state quitline.

Smokers receiving the intervention will be sent from 0 and 5 text messages per day. This is the message volume used by most smoking cessation text messaging programs.⁶⁰ Smokers are asked to enter a quit date in the first 30 days after enrollment. Those without a quit date will be sent the practice quit attempt messages. At the end of the practice quit attempt messages subjects will be asked again if they have a quit date in the next 30 days. For those who are ready to quit at time of enrollment, or those who become ready to quit after the practice attempt, up to 5 messages per day are delivered in the 2 weeks leading up to the self-designated quit

date and the 2 weeks after the quit date when they are at greatest risk for relapse.⁶¹ Messages then decrease to 3 messages per week for 8 weeks after the attempt.

b. Drugs used

Subjects randomized to the NRT or TM + NRT arms will be offered nicotine replacement therapy dependent on their smoking patterns and readiness to quit.

Daily smokers planning to quit in the next 30 days will be offered combination nicotine replacement therapy including nicotine patches and nicotine lozenges. Daily smokers will be offered nicotine patches (14 or 21 mg patches) and lozenges (2 or 4 mg lozenges). Smokers who smoke ≥ 10 cigarettes per day will be offered 21 mg patches, those who smoke < 10 cigarettes per day will be offered 14 mg patches. Daily smokers who smoke within 30 minutes of awakening will be also offered the 4 mg lozenges. Daily smokers who smoke > 30 minutes of awakening will be offered 2 mg lozenges. Daily smokers with a prior reaction to adhesives from bandaids or the nicotine patch will be offered lozenges only.

Smokers not planning to quit will be offered one box of lozenges (72 count box of 4 mg or 2 mg lozenges based on time to first cigarette as above per package instructions) to use when they are not smoking during their practice quit attempt⁵³.

The efficacy and safety of mailing nicotine replacement therapy to general population has recently been demonstrated⁵⁵.

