The sample of smokers enrolled in the study will be characterized on baseline measures from the EHR and compared to the population of smokers whom we attempted to contact in order to determine the sample's representativeness to the target population. Variables include demographics, medical history, and practice characteristics. We will also compare baseline characteristics collected from the EHR and from baseline interviews between the 4 randomized groups to determine the success of randomization. The primary outcome analysis will be conducted as intention-to-treat, comparing the primary outcome using chi-square analysis or multiple logistic regression analysis if any baseline factor is significantly imbalanced by group ($p<0.05$) as independent variables. The 4 arm design allows for analysis as a factorial design. We will first test for interaction between the NRT and TM interventions and if no interaction is detected we will test the effect of text messaging using both TM and TM+NRT arms compared to BA and NRT arms. If interaction is present, we will compare the TM arm to BA for our primary analysis. We will secondarily compare the groups in terms of self reported 7 day PPA, biochemically confirmed abstinence, number of days not smoked, use of ≥ 1 evidence based treatments, and cigarettes per day using chi-square or t-tests or logistic or linear regression if groups are imbalanced. We will also compare the TM+NRT group with the NRT group in terms of total days of medication used and total mg of medication used over 2 weeks using linear regression. We will conduct stratified analyses of the primary outcome, 7 day PPA, treatment use and days not smoked by readiness to quit in the next 30 days.

Sample size

Hypothesis 1: A 12 week text messaging intervention (up to 30 days pre-quit through 8 weeks post-quit) providing behavioral support will increase the proportion of smokers making a quit attempt compared to a control group receiving brief advice.

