The sample size for this pilot study is selected to adequately estimate recruitment rates, retention, and to get a preliminary estimate of prevalence of clinical outcomes. We anticipate we can recruit 200 patients by proactive outreach over 12 months. With 50 patients per group and 25% loss to follow-up we will have 81% power to detect a relative risk of self-reported ≥ 24 hour quit attempts of 1.8 for text messaging versus brief advice groups. We base this estimate on meta-analyses of smoking cessation text messaging trials, mostly from community settings or school-based settings, report a relative risk of 1.4 for 7-day point prevalence abstinence and 1.6 for prolonged abstinence measured at six-months.^{8,71}

Hypothesis 2: A 12 week text messaging intervention providing personalized, tailored behavioral support and advice about using nicotine replacement therapy (NRT) plus 2 weeks of NRT mailed to the participant will increase adherence to NRT compared to subjects receiving only 2 weeks of NRT as measured by duration of NRT use in days.

For our secondary outcome of medication adherence, we estimate patients randomized to the NRT will use a mean 9 days of medication based on the offer to mail them 2 weeks of medication for free.⁷² With this sample size, we also have 80% power to detect an increase in days of NRT use from 9 to 12 days in NRT vs. NRT+TM.

Hypothesis 3: A 12 week text messaging intervention will increase the rate of *biochemically confirmed* past 7-day point prevalent tobacco abstinence at end of treatment compared to subjects receiving no text messaging intervention.

We do not expect to have power to detect cessation in this pilot study. With 100 subjects and 25% loss to follow-up we will have 80% power to detect an increase from 6% among the BA & NRT groups to 22% in TM & TM + NRT groups.

Regardless, this pilot study aims to generate an estimate of effect size on cessation at 12 weeks for further studies.

Hypothesis 4: A 12 week text messaging intervention will increase the number of days not smoking compared to subjects receiving no text messaging intervention.

Assuming $\alpha=0.05$ and 25% loss to follow-up, leaving 75 patients, we have 68% power to detect an increase in days not smoked from 0.2 in groups receiving no text messaging (BA & NRT) to 1 in groups receiving text messaging (TM & TM + NRT) assuming a standard deviation of 2.

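### Hypothesis 2 pools ready and not-ready smokers on days and mg of NRT, but its 9-to-12-day assumption fits only a full two-week course

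*Combined protocol and SAP*

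**What the plan says.** Section II defines Hypothesis 2 by two measures of adherence: days of NRT use and total mg used. Section VI, Data analysis, compares the TM+NRT group with the NRT group on "total days of medication used and total mg of medication used over 2 weeks", by linear regression, with no restriction or adjustment for readiness to quit. Section VI, Sample size, assumes that the NRT arm "will use a mean 9 days of medication based on the offer to mail them 2 weeks of medication for free" and states "80% power to detect an increase in days of NRT use from 9 to 12 days in NRT vs. NRT+TM". It gives no SD for this outcome and no expected days by readiness. The arm size comes from the same section: "With 50 patients per group and 25% loss to follow-up".

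Section IV.a enrols smokers who are ready to quit within 30 days and smokers who are not. For the not-ready, the text-message content offers "tips to try a practice quit attempt for a few hours or days". Under Section V.b, ready daily smokers in the NRT arms are offered patches and lozenges. Not-ready smokers are offered one 72-count box of lozenges "to use when they are not smoking during their practice quit attempt". The same section tells participants not to use either product while smoking.

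Section IV.c stratifies randomization by practice and by readiness. The readiness-stratified analyses in Section VI cover the primary outcome, 7-day abstinence, treatment use and days not smoked. Days and mg of NRT are not named. Section I.b reports that 32% of those who opted in to the pilot were not ready to quit.

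**The concern.** In the ready stratum, more days of NRT within the two weeks means better adherence to the offered course. In the not-ready stratum it need not. A patient told to use lozenges only while not smoking, during a practice attempt, may follow that instruction fully with few days of use. The mg measure has the same difficulty, because the supply differs by stratum. A pooled mean therefore mixes two kinds of use.

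Two things are at stake. The planned 12-day mean may not suit the mix of patients enrolled, and an adherence effect confined to ready smokers would be diluted. A null pooled result could then be read as text messaging failing to improve adherence. Section IV.c gives testing that effect as the reason for having both NRT arms.

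**Working it through.** **Inputs.** From Section VI: means of 9 and 12 days, 80% power, 50 per arm with 25% loss (50 × 0.75 = 37.5 evaluable per arm), and a two-week window (at most 14 days). From Section I.b: not-ready share s = 0.32, a pilot figure. Assumed: two-sided alpha of 0.05 (Section VI states 0.05 only for Hypotheses 4 and 5, without sides), and d, the mean NRT days of not-ready smokers, which the protocol does not give.

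**1. The stated 80%.** It cannot be reproduced directly, because no SD is given. Solving a two-sample t-test for the SD that gives 80% power for 3 days at 37.5 per arm yields about 4.6 (4.58). Without loss to follow-up, at 50 per arm, it is about 5.3. Either is possible for a 0–14 day count, so the 80% is not contradicted.

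**2. Ceiling on the arm mean.** If every ready smoker uses NRT on all 14 days, the highest arm mean is (1 − s) × 14 + s × d. At s = 0.32:

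| d (days) | Highest arm mean |
|---|---|
| 1 | 9.84 |
| 3 | 0.68 × 14 + 0.32 × 3 = 10.48 |
| 5 | 11.12 |
| 7 | 11.76 |

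A mean of 12 requires d ≥ (12 − 0.68 × 14) / 0.32 = 7.75 days. At s = 0.20 the requirement is 4.0 days, and at s = 0.15 it is 0.67 days, still with every ready smoker at 14 of 14. The largest share that permits a mean of 12 is 2 / (14 − d): 14.3% at d = 0, 18.2% at d = 3 and 28.6% at d = 7.

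The 9-day control mean is less demanding. At s = 0.32 and d = 3, ready smokers would need (9 − 0.32 × 3) / 0.68 = 11.8 days.

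**3. Dilution.** If ready smokers go from 9 to 12 days and not-ready smokers do not change, the pooled difference is 0.68 × 3 = 2.04 days. At 37.5 per arm and SD 4.58, power is about 48%.

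The pooled SD would probably exceed the within-stratum SD. As an illustration, take SD 4.64 in ready smokers, SD 2 in not-ready smokers and d = 3 in both arms. The variance in each arm is 0.68 × 4.64² + 0.32 × 2² + 0.32 × 0.68 × (ready mean − 3)². This gives 23.7 in the NRT arm (ready mean 9) and 33.6 in the TM+NRT arm (ready mean 12). The average is about 28.6, an SD of 5.35, and power is about 38% (normal approximation). The between-stratum terms are 7.8 and 17.6, averaging 12.7, or about 44% of that variance. A readiness covariate would remove most of it.

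**4. Ready stratum alone.** 37.5 × 0.68 = 25.5 evaluable per arm. Power for a 3-day difference is about 63% at SD 4.6 and about 75% at SD 4.0.

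**5. Supply in mg.** A 72-lozenge box holds 72 × 2 = 144 mg or 72 × 4 = 288 mg. Ready smokers are offered 14 or 21 mg patches as well as lozenges. Assuming one patch a day for 14 days, the patches alone come to 196 or 294 mg. The most that can be used therefore depends on stratum.

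**The case against.** A reader might infer that the 12-day target is unattainable. The documents do not support that. No section caps lozenge days. The phrase about hours or days describes one practice attempt, while Section IV.c speaks of attempts in the plural and of a two-week allotment. A box of 72 spread over 14 days is about 5 lozenges a day. Not-ready smokers in the text arms are asked again about a quit date (Section V.a). The 32% comes from a pilot recruited by letter and a single opt-in text. This trial uses telephone outreach, a website advertisement and inpatient referral, so its share could be lower or higher.

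A reader might also infer that the 80% is wrong, or that 48% or 63% is the true power. Neither follows. The SD is back-solved from the claim itself, and a whole-arm SD need not hold within one stratum. The 48% further assumes no text-message effect in not-ready smokers. That the 9-day mean describes ready smokers is an inference from its stated basis, a two-week supply.

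Nor do the documents oblige the trial to restrict Hypothesis 2 to ready smokers. Comparing whole randomized arms is a legitimate estimand, and stratified randomization guards the pooled contrast against imbalance in readiness. This is a secondary outcome in a pilot sized mainly to estimate recruitment, retention and outcome prevalence.

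These points limit the claim but do not remove it. The planned stratified analysis of treatment use helps only partly. It most naturally refers to the use of at least one evidence-based treatment, named shortly before it, and in any case it does not name days or mg. The ceiling is also generous: ready smokers may set a quit date up to 30 days after enrolment (Section V.a) and are told not to use NRT while smoking, so some of their use may fall outside the two weeks.

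**Conclusion.** The point holds as a mismatch between the Hypothesis 2 measure and part of the randomized population. The planned means fit a full two-week course, and the plan makes no allowance for not-ready smokers, whose offered product, supply and intended use differ. If the pilot's 32% applied here, the 12-day mean would need substantial lozenge use, at least 7.75 days on average, from smokers not planning to quit. With an assumed 3 days, the ceiling is about 10.5. An effect confined to ready smokers would shrink to about 2.0 days when pooled. The size of the problem depends on three quantities that the plan leaves open: the not-ready share, not-ready lozenge days and the SD. It is worth correcting because adherence is a named aim and the remedy uses the existing design.

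**What to change.** - **Data analysis (Section VI):** fit the Hypothesis 2 linear regressions for days and for mg with readiness as a covariate. Add medication days and mg to the list of readiness-stratified analyses, so that the ready-stratum estimate, where a two-week course is intended, appears beside the not-ready one. The pooled comparison can stay.
- **Sample size (Section VI):** say that 9 to 12 days is an assumption for ready smokers. Give the SD, its source and the expected not-ready share. State power conditionally: for 3 days in the ready stratum at 25–26 evaluable per arm (a 32% not-ready share), about 63% at SD 4.6 and about 75% at SD 4.0.
- **Not-ready smokers:** report the lozenge days and counts already collected at weeks 1 and 2. Do not define a measure of use on non-smoking days: the surveys in Section V.d record lozenge days and smoking days as separate weekly counts that cannot be linked by day.

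The cost is a few sentences in Section VI and no new data. The drawback is that the stated power may become less favourable.

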 - How many days in the past 7 days did you use nicotine lozenges?
 - On days when you use lozenge, how many do you use on average?
- Since starting the study, have you stopped smoking cigarettes for 1 day or longer because you were trying to quit smoking?
 - If yes→In the past 30 days, how many days did you not smoke cigarettes?
 - If yes→On how many of the past 7 days did you have at least one cigarette?
If 0→Have you smoked cigarettes, even a puff in the past 7 days?
- Have you experienced any side effects in the past 30 days from quit smoking medications?
- Receipt of text messages since last assessment

12 week end-of-treatment telephone outcome assessment

Quit attempt and smoking cessation outcomes will be assessed by telephone at 12 weeks (end of treatment)

PRIMARY OUTCOME: Self-reported quit attempt in the last 12 weeks defined as intentional not smoking for 24 hours or more ("Since the start of the study, have you quit smoking intentionally for 1 day or longer" in addition to past follow up reports of quit attempts). We recognize that tobacco abstinence for more than one day is the desired outcome but feel this intermediate outcome is appropriate in the context of a pilot study with limited resources.

SECONDARY OUTCOMES:

How many times did you try to quit during the study?

Have you smoked, even a puff, in the past 7 days? (7 day PPA)

In the past 30 days, how many days did you not have a cigarette?

How many cigarettes do you now smoke per day?

Motivation to quit, confidence to quit, and perceived 2-week distress measured using single-item instruments with 11-item likert scale

Use of evidence based treatment and behavioral treatment in the past 12 weeks (NRT, varenicline, bupropion, clinic or class, in-person counseling, telephone counseling, text messaging, alternative therapy, self help materials, or online communities and applications)

Past month use of other tobacco products including electronic cigarettes

Side effects of quit smoking medications in the past 12 weeks

Satisfaction with treatment

Exhaled CO in ppm among subjects reporting 7 day PPA

Up to 10 attempts will be made to reach study subjects for each outcome assessment (weeks 1, 2, 6 and 12).

Measures of intervention utilization:

Intervention utilization will be obtained from MobileCommons software.

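### Hypotheses 3 and 4 use incompatible control-group values: 6% abstinent at week 12 implies a mean of at least 0.42 smoke-free days, but Hypothesis 4 assumes 0.2

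*Combined protocol and SAP*

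**What the plan says.** Both planning statements are in section VI, under Sample size, and concern the same pooled comparison: BA and NRT against TM and TM+NRT.

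- **Hypothesis 3.** The endpoint is biochemically confirmed "past 7-day point prevalent tobacco abstinence at end of treatment compared to subjects receiving no text messaging intervention". The power statement is for "an increase from 6% among the BA & NRT groups to 22% in TM & TM + NRT groups", with 100 subjects, 25% loss and 80% power.
- **Hypothesis 4.** "Assuming $\alpha=0.05$ and 25% loss to follow-up, leaving 75 patients", the plan says "we have 68% power to detect an increase in days not smoked from 0.2 in groups receiving no text messaging" (BA and NRT) "to 1 in groups receiving text messaging (TM & TM + NRT"), with a standard deviation of 2. The paragraph gives neither the recall window nor the assessment week for days not smoked.

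The measurements are defined in section V.d, in the list of secondary outcomes for the 12-week telephone assessment. Abstinence is taken from "Have you smoked, even a puff, in the past 7 days? (7 day PPA"). Smoke-free days are taken from "In the past 30 days, how many days did you not have a cigarette". Exhaled CO is measured only in those who report 7-day abstinence.

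**The concern.** The two week-12 questions are asked in the same interview, and the 7-day window lies inside the 30-day window. A person with no puff for 7 days has had no cigarette on any of those days, and so has at least 7 smoke-free days out of 30. The abstinence rate therefore puts a floor under the mean number of smoke-free days. The control mean in Hypothesis 4 lies below the floor set by the control rate in Hypothesis 3.

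What is at stake is the Hypothesis 4 power statement. Its 68% is calculated for a control group that the preceding hypothesis rules out.

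**Working it through.** **Inputs.** Control abstinence 6% (Hypothesis 3). Control mean 0.2, text-messaging mean 1, SD 2, alpha 0.05, 75 analysed (Hypothesis 4). At least 7 smoke-free days per abstainer (the two week-12 items in section V.d). Sidedness is not stated; two-sided is assumed.

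**1. Reproduce the stated power.** With 75 per pooled group, the standard error of the difference is 2 × √(2/75) = 0.327. The difference is 1 − 0.2 = 0.8, and 0.8/0.327 = 2.45. The normal approximation gives Φ(2.45 − 1.96) = 68.8%, and the two-sample t-test gives 68.2%. The stated 68% is reproduced. A one-sided test would give 78.9%, and 75 patients in total would give 41.0%, so the plan used 75 per pooled group and a two-sided test.

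**2. Check that Hypothesis 3 has the same denominator.** 6% against 22% with 75 per group gives 81.3%, against the stated 80%. Both statements fit 75 per pooled group.

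**3. Floor on the control mean.** Mean days ≥ 7 × P(7-day abstinent) = 7 × 0.06 = 0.42. This supposes that every non-abstainer has no smoke-free day and every abstainer has exactly 7, so it is the lowest possible value.

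**4. The same bound in reverse.** A mean of 0.2 allows at most 0.2/7 = 2.9% abstinent.

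**5. In people and days, for 75 controls.**

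| Assumption | Abstainers | Smoke-free days in total |
|---|---|---|
| Hypothesis 4, mean 0.2 | at most 15/7 = 2.1 | 75 × 0.2 = 15 |
| Hypothesis 3, 6% | 75 × 0.06 = 4.5 | at least 4.5 × 7 = 31.5 |

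**6. Two checks on the floor.** Confirmed abstainers are a subset of those who report abstinence, so self-reported abstinence is at least 6% and the floor is not weakened. If the 4.5 abstainers are spread over all 100 randomised, with dropouts counted as zero days, the floor is 4.5 × 7/100 = 0.315, still above 0.2.

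**7. Effect on power if only the control mean changes.** The difference becomes 1 − 0.42 = 0.58, and 0.58/0.327 = 1.78. Power is Φ(1.78 − 1.96), about 43%, or 42% by the t-test.

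**8. Other consistent inputs give other answers.** With 0.42 against 1.22 and SD 2, the difference is again 0.8 and power stays at 68%. With 6% against 22% abstinent, each abstainer at 7 days and everyone else at 0, power is about 82%. These are illustrations, not values to print.

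**The case against.** The strongest objection is that the Hypothesis 4 paragraph never says what its days refer to. Section V.d also has smoking-day questions at weeks 1, 2 and 6, and a week-12 abstinence rate does not constrain those. Nor does the floor hold for a rate. If the 30-day count were re-expressed as days per week, an abstainer with exactly 7 days would score 7 × 7/30 = 1.63, and the control floor would be 0.06 × 1.63 = 0.098, below 0.2. What stands is that the link to the week-12 item is an inference, and the conclusion depends on it. It is the natural inference: that item is the only smoke-free-day outcome listed at week 12, and no rescaling appears anywhere in the documents.

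It is also fair to say that little turns on this. Hypothesis 4 is secondary, its power is already declared below 80%, and the pilot is sized to estimate recruitment, retention and preliminary outcome rates. That limits the importance of the point but does not reconcile the two figures.

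Three stronger readings are tempting, and the documents do not support them:

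- *The text-messaging means conflict as well.* At 22% the floor is 0.22 × 7 = 1.54, against 1. But 22% is the alternative that Hypothesis 3 could detect, and Hypothesis 4 may be powered for a different effect. The 6% is different in kind, because it is the assumed starting level of the control groups.
- *The SD of 2 is wrong.* No source is given for it, but the same is true of other planning values in this section. With 6% at exactly 7 days and the rest at 0, the control SD is 7 × √(0.06 × 0.94) = 1.66, so 2 is not excluded.
- *The true power is below 68%.* Step 8 of the working shows that it can be lower, the same or higher, depending on how the other inputs are reset.

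**Conclusion.** The point holds for the control groups at week 12. The assumed mean of 0.2 is less than half the minimum of 0.42 that 6% abstinence implies, and the two values cannot both describe BA and NRT. The 68% contains no calculation error; the fault is in one of its inputs. With that input alone moved to its minimum, power is about 42%.

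The conclusion rests on reading days not smoked as the week-12 count over the past 30 days, and on both paragraphs referring to the same analysed patients, which the reproduced powers support. It needs no outside data. It is a minor correction to a secondary power statement.

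**What to change.** Revise the Hypothesis 4 paragraph as follows:

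1. State that days not smoked is the week-12 count over the past 30 days.
2. Make the control assumptions agree. Either use a control mean consistent with the Hypothesis 3 rate (at least 0.42 at 6%), or state a lower control abstinence rate in Hypothesis 3 and restate the power there. Keeping 0.2 requires a rate of 2.9% or less.
3. Restate the detectable difference and the power for Hypothesis 4 with the inputs chosen.

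The cost is one rewritten paragraph, plus a change to the Hypothesis 3 paragraph if its rate is the one altered. The stated power for Hypothesis 4 may become less favourable. Sample size, trial conduct and the primary analysis do not change.
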